## RELIEF TRIAL PROTOCOL SUMMARY

Title	Safety and Feasibility of Adipose Derived Regenerative Cells (ADRCs) in the Treatment of Deep Partial Thickness and Full Thickness Thermal Wounds (RELIEF)
Test Product	Celution® System used for processing of Autologous Adipose-Derived Regenerative Cells (ADRCs)
Objective	The primary objective of the protocol is to evaluate preliminary safety and feasibility of ADRCs via intravenous delivery in the treatment of deep partial and full thickness thermal wounds.
Design	A prospective, open-label, parallel group, usual care controlled, multi-center randomized (2:1, active: usual care alone) safety and feasibility study targeting thermal burns. Subjects will have at least one deep partial or full thickness burn wound of $\geq 250 \text{ cm}^2$ that is to be autografted with a meshed split thickness skin graft (STSG) Subjects randomized to ADRCs will undergo small volume fat harvest (100 to 150 mL) performed under general anesthesia during scheduled burn surgery followed by peripheral intravenous delivery of ADRCs within 4 hours of completion of Celution® processing. Harvested tissue will be processed in the Celution® System to isolate and concentrate ADRCs. Subjects randomized to usual care will not undergo a fat harvesting procedure.
Sample Size	Up to 15 subjects will be enrolled. Each subject will contribute up to three qualified wound areas for the analysis.
Enrollment	The 1st 5 subjects enrolled in active treatment will be observed for adverse events over a 7 day period. If no SAEs occur during that period, for that individual subject, the next subject enrolled in active treatment may be entered with the same 7 day observation period. The safety results of the first 5 subjects will be reviewed by the DMC and their evaluation will be used in conjunction with the clinical data collected to date, and if appropriate, to potentially remove the staggering approach to the study. Enrollment after the first 5 subjects enrolled in active treatment may continue only after the DMC has completed its safety review and recommends continuation.
Study Location	Up to 10 regional burn centers in the US
Indication	Celution® System is intended for the preparation of autologous adipose-derived regenerative cells (ADRCs) for intravenous use as an adjunct to autologous split thickness skin grafts used in the current standard treatment of full thickness and deep partial thickness thermal burn injuries
Post Procedure Evaluations	Evaluations at early dressing changes (time of first dressing change, day 10 ( $\pm 2$ ) days and weeks 2 ( $\pm 3$ days), 3 ( $\pm 3$ days), 4 ( $\pm 3$ days), 8 ( $\pm 7$ days), 12 ( $\pm 14$ days), 26 ( $\pm 14$ days) and 52 ( $\pm 21$ days) post-grafting
Treatment Arm	Adjunct to thermal burn skin wound coverage with autologous meshed split thickness skin graft (STSG) delivered intravenously on the same day as STSG. Dose: $20 \times 10^6$ ADRCs

Primary Endpoint	Safety and Feasibility 
 
Safety will be evaluated based on the incidence, type and seriousness of adverse events related to the IV administration of test substance as well as the low volume lipoharvest procedure.
 
Feasibility will be determined as the ability to obtain > 100 mL adipose tissue, obtain <math>\geq 20 \times 10^6</math> ADRCs, and deliver the prepared cell dose.
 

Key Secondary Endpoints	
 
Percent epithelialization of the graft at time of first dressing change, day 10 and weeks 2, 3 and 4 post grafting (assessed by surgeon visual evaluation and blinded independent review of standardized photographs)
 
Percent take of the graft at time of first dressing change and day 10 and weeks 2, 3 and 4
 
Percent of group with complete wound healing at weeks 2, 3, 4, 8 and 12
 

Exploratory Endpoints	
 
Transepithelial water loss at weeks 2, 3 and 4 to be performed at 2 different sites within the wound (central and peripheral)
 
Wound pain VAS (visual analogue scale) at time of first dressing change and day 10 and weeks 2, 3 and 4
 
Pruritis VAS at weeks 3, 4, 8, 12, 26 and 52
 
Patient and Observer Scar Assessment Scale (v2.0) at weeks 3, 4, 8, 12, 26 and 52
 
Skin elasticity measurement at weeks 12, 26 and 52
 
Vancouver Scar Scale at weeks 12, 26 and 52
 
Skin pigmentation and hardness at weeks 12, 26 and 52
 
ADRC cell population subtypes (FACS)
 
Biomarkers related to burn injury (such as C-reactive protein (CRP), IL-6, IL8, IL1<math>\beta</math>, interleukin-1 receptor antagonist (IL-1ra); neutrophil gelatinase-associated lipocalin (NGAL); Tumor Necrosis Factor-<math>\alpha</math> (TNF<math>\alpha</math>), and tumor necrosis factor receptor 1a (TNFR-1a)) and related to scarring (such as amino-terminal propeptide of type III procollagen, (PIIINP), TIMP1, MMP2, MMP9 and VEGF-A) will be collected at baseline (prior to treatment), days 6, and 10 and weeks 2, 3, 4, 8, and 12 post ADRC administration. Serum sample will be collected from 4 to 5 ml of whole blood that is centrifuged, separated into 500-<math>\mu</math>L aliquots, and stored at -80°C at the clinical site serum bank or central lab until use.
 
Serum biomarkers will be measured using commercial Enzyme-Linked ImmunoSorbent Assay (ELISA).
 

Statistics	
The intent-to-treat (ITT) population will include all randomized subjects. Randomization will occur on the STSG procedure day prior to liposuction. The per-treatment-evaluable (PTE) population will include all enrolled subjects who have day 6 follow-up information available.
 
The groups compared will be the subjects receiving ADRCs and STSG and the usual care controlled subjects (both grouped and stratified by mesh size). Analysis will be performed by a one way ANOVA.

Inclusion & Exclusion Criteria	
Inclusion Criteria
 
 
1. Males or females age <math>\geq 18</math> to <math>\leq 65</math>
 
2. BMI <math>> 20 \text{ kg/m}^2</math>
 
3. Burn TBSA 20% - 50%
 
4. At least one deep partial thickness and/or full thickness thermal burn <math>\geq 250 \text{ cm}^2</math> on the arms, legs, back, abdomen or chest that is anticipated to be covered with a meshed autologous STSG and that has not been treated previously with a biologic dressing such as AlloDerm® or Integra®
 
5. Ability to safely undergo tissue harvest that is anticipated to yield <math>>150 \text{ mL}</math> of adipose tissue at a site that is free from infection
 
6. Donor site availability for skin graft harvest
 
7. Able to provide written informed consent signed by either the patient or their legally authorized representative
 
8. Women and men of child-bearing potential agreeing to use contraception during the study. Acceptable methods include surgical sterility, IUDs, hormonal contraception or double barrier methods.
 

	
Exclusion Criteria
 
 
1. Subjects with burns <math>> 3^{\text{rd}}</math> degree (i.e. involvement of deeper tissues, such as muscle, tendons, or bone)
 
2. Subjects with electrical or chemical burns
 
3. Subjects with significant inhalation injuries necessitating intubation and mechanical ventilation or requiring <math>> 50\%</math> FiO2 on a continuous basis to maintain oxygenation (O2 sat <math>> 90\%</math>)
 
4. In the opinion of treating physician, patient not expected to survive beyond 30 days
 
5. Pre-existing condition requiring current use of immunosuppressive medication or systemic steroids
 
6. Pregnant or lactating status. Pregnancy as determined by a positive pregnancy test at screening or baseline
 
7. Known history of HIV infection, or active Hepatitis B or active Hepatitis C infection
 
8. Cancer requiring chemotherapy or radiation within previous 6 months or resection within the last 5 years (other than basal cell carcinoma)
 
9. Known chronic renal failure (serum creatinine <math>> 2 \text{ mg/dL}</math>) or chronic liver disease
 
10. Pre-existing medical conditions that would interfere with wound healing (i.e., diabetic patients with Hemoglobin A1c <math>\geq 8.0\%</math>, malignancy, autoimmune disease)
 
11. Subjects with psychiatric conditions that are anticipated to result in protocol noncompliance
 
12. Chronic illicit drug or alcohol abuse that is anticipated to interfere with patient compliance with the protocol
 
13. Participation in another clinical trial within 60 days of the screening visit
 
14. Any concurrent disease or condition that, in the opinion of the investigator, would make the patient unsuitable for participation in the study
 

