## 4.3 Sample Size

Up to a total of 15 subjects will be enrolled. Each patient may contribute up to three qualified wound

areas for the analysis. If more than one wound is identified, each must be noncontiguous with the other(s). Therefore, between 15 and 45 wounds will be evaluated. Wound areas that have been treated with a biologic dressing such as Alloderm® or Integra® are not qualified for analysis. However, a wound area that receives excision and grafting as described in this protocol without the application of a biologic dressing may be qualified even if other wound areas in the subject are not qualified because they have been treated with a biologic dressing.

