##### ***4.6.2 Key Secondary Endpoints***

- Percent epithelialization of the graft at time of first dressing change and day 10 (only if wound dressing change planned) and weeks 2, 3 and 4
- Percent take of the graft at time of first dressing change and day 10 (only if wound dressing change planned) and weeks 2, 3 and 4

Digital photography will be performed at surgery and at each follow-up visit for blinded independent review.

Graft take will be assessed as the area over which vascularization is evident and sufficient anchorage to the underlying tissue exists to support epidermal growth. Take will be expressed as a percentage of the area originally covered by the graft. Percent take should be estimated separately for each graft-treated site.

Both of the above endpoints will be evaluated by (a) visual inspection by the treating surgeon, and (b) standardized digital photography and scoring centrally by a blinded trained assessor.

- Percent of group with complete wound closure at each assessment through to 12 weeks

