## 5.2 Randomization and Subject Identification

Randomization to ADRC and usual care will occur within 2 hours prior to the scheduled surgery for STSG.

Randomization will be done via an interactive web response system (IWRS). Subjects will be randomized in a 2:1 ratio to receive intravenous delivery of either Celution® System processed ADRCs with usual care or to usual care alone.

A total of up to 15 subjects will be enrolled. Each patient will contribute up to three qualified wound areas for the analysis. If more than one wound is identified, each must be noncontiguous with the other(s). Therefore, between 15 and 45 wounds will be evaluated.

The 1st 5 subjects enrolled in active treatment will be observed for adverse events over a 7 day period. If no SAEs occur during that period, for that individual subject, the next subject enrolled in active treatment may be entered with the same 7 day observation period. The safety results of the first 5 subjects will be reviewed by the DMC and their evaluation will be used in conjunction with the clinical data collected to date, and if appropriate, to potentially remove the staggering approach to the study. Enrollment after the first 5 subjects enrolled in active treatment may continue only after the DMC has completed its safety review and recommends continuation.

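### Up to three wounds per randomised subject enter the efficacy dataset with no rule giving one value per subject, and complete closure is counted per wound in one section and per subject in another

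*Protocol*

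**What the plan says.** Assignment is by subject. Section 5.2 states "Subjects will be randomized in a 2:1 ratio to receive intravenous delivery", and section 7 describes one infusion into a peripheral vein, so all wounds of a subject share one assignment.

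Data come by wound. The Summary says "Each subject will contribute up to three qualified wound areas for the analysis", section 4.3 concludes "Therefore, between 15 and 45 wounds will be evaluated", and section 10.2 repeats that each subject brings up to three wounds to the dataset. For graft take, section 4.6.2 says "Percent take should be estimated separately for each graft-treated site".

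On the test, the Summary says "The groups compared will be the subjects receiving ADRCs and STSG and the usual care controlled subjects (both grouped and stratified by mesh size" and then "Analysis will be performed by a one way ANOVA". Section 10.3 repeats the stratification by mesh size, which it describes as a feature of the grafts. It also names Student's t-test for change from baseline and sets two-sided testing at 0.05.

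Complete closure is described in several ways:
- Summary: "Percent of group with complete wound healing at weeks 2, 3, 4, 8 and 12".
- Section 4.6.2: "Percent of group with complete wound closure at each assessment through to 12 weeks".
- Section 8.3: a percentage of wounds.
- Section 10.3.2: a proportion of subjects.

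**The concern.** Wounds on one person share that person's burn, general condition, surgeon and treatment assignment, so they are likely to heal alike. A test that takes each wound as a separate observation would then understate the standard error, and a chance difference between about 10 and 5 people could look nominally significant. The text leaves room for this: the dataset is counted in wounds, the strata follow the graft, and nothing says how two or three wounds become one observation.

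Closure is a plainer problem. The same results give different percentages depending on the section followed, and a subject with one wound closed and another open cannot be classified.

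What is at stake is modest but real. Section 10.3.2 counts exploratory p-values towards the overall evidence on the product, and section 10.2 says the study will inform the design of a larger one.

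**Working it through.** **The plan's own count.** 15 subjects × 1 wound = 15 and 15 × 3 = 45, which reproduces section 4.3. At 2:1, 15 subjects split into 10 and 5. The plan has no power calculation to reproduce.

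**Inputs.** From the protocol: 10 versus 5 subjects, k = 1 to 3 wounds each, two-sided 0.05, and an ANOVA with treatment group as its only factor. Assumed, because the protocol gives no figure: a within-subject correlation (ICC) of 0.1 to 0.9, with normal errors.

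**Error rate if the test is run on wounds.** Let L1 = 1 + (k − 1) × ICC and L2 = 1 − ICC. With no treatment effect:
- group mean square ~ L1 × χ²(1);
- residual sum of squares ~ L1 × χ²(13) + L2 × χ²(15(k − 1));
- the ratio is referred to F(1, 15k − 2).

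Hand check for k = 3, ICC 0.3. L1 = 1.6 and L2 = 0.7. The expected residual mean square is (1.6 × 13 + 0.7 × 30)/43 = 0.972. The reported standard error is about √(0.972/1.6) = 0.78 of the true one. The critical value 2.017 acts like 2.017 × 0.78 ≈ 1.57, which on 43 degrees of freedom is exceeded about 12% of the time.

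Simulated rejection rate at nominal 5%:

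| Wounds per subject | ICC 0.1 | 0.2 | 0.3 | 0.5 | 0.7 | 0.9 |
|---|---|---|---|---|---|---|
| Three each | 7.4% | 9.9% | 12.5% | 17.5% | 22.2% | 26.6% |
| Two each | 6.2% | 7.5% | 8.7% | 11.5% | 14.3% | 17.1% |
| Mix of one to three | 6.5% | 8.1% | 9.7% | 13.1% | 16.7% | 20.0% |
| One each | 5% | 5% | 5% | 5% | 5% | 5% |

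Inside one mesh stratum, assuming 6 versus 3 subjects with two wounds each of that mesh size, the rates run from 6.2% to 18.5% over the same ICC range.

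The effective number of wounds with three each is 45/(1 + 2 × ICC): 37.5 at ICC 0.1, 22.5 at 0.5 and 16.1 at 0.9.

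**Error rate on one value per subject.** The same test on subject means has 15 − 2 = 13 error degrees of freedom instead of 45 − 2 = 43, and rejects 4.7% to 5.3% of the time in every case run.

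**Closure.** Assume 70% of wounds closed and a beta-binomial model with ICC 0.2 or 0.7.
- Two wounds: mixed results occur with probability 2 × 0.7 × 0.3 × (1 − ICC) = 0.336 at ICC 0.2 and 0.126 at ICC 0.7.
- Three wounds, ICC 0.2 (beta parameters 2.8 and 1.2): all closed = 2.8 × 3.8 × 4.8/(4 × 5 × 6) = 0.426. None closed = 1.2 × 2.2 × 3.2/120 = 0.070, so any closed = 0.930 and mixed = 0.504.
- Three wounds, ICC 0.7: all closed 0.603, any closed 0.792, mixed 0.189.

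So 70% of wounds corresponds to 43-60% of three-wound subjects if all wounds must close, and to 79-93% if any one suffices.

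**The change-from-baseline t-test.** Appendix A first lists epithelialization, take and wound pain at the first dressing change, water loss and closure at week 2, and scar measures at week 3 or 12. It schedules no baseline score for any of these. With two groups the pooled t-test gives the same p-value as the ANOVA, so running it on wounds would have the same effect.

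**The case against.** The strongest reply is that the protocol already makes the subject the unit. The Summary and section 10.3 speak of comparing subjects, section 10.3.2 of a proportion of subjects, and section 10.5 defines the intent-to-treat population by randomised subjects. A reader might infer that a wound-level ANOVA is prescribed, or that ANOVA is the wrong test. Neither is supported. On one value per subject a two-group ANOVA is valid and identical to a two-sample t-test. This part of the reply stands, and the inflation figures are therefore conditional.

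A reader might also infer that no wound endpoint has a baseline, so that the t-test in section 10.3 cannot apply to wounds. Appendix A points that way, but section 4.6.2 sends the photograph taken at surgery to blinded review. Whether it is scored is unclear, not settled.

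A third reply is that summarising wounds within a subject is ordinary analysis-plan content, and section 10.1 leaves detail to a separate plan that is not shown. That plan may well supply the rule, which limits the weight of the first part. It does not remove the point, because the protocol itself counts the dataset in wounds and names the test without saying what one observation is. Nor would it remove the closure conflict, since both units would still stand in the protocol. It is fair that section 8.3 is an assessment list and that the wording about the group in the Summary and section 4.6.2 is compatible with subjects. Even so, no section says how mixed results count.

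Finally, these endpoints are secondary or exploratory, the study is declared unpowered, and its p-values are nominal. That lowers the severity.

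**Conclusion.** The point holds in two parts. First, the protocol does not fix the unit of inference for wound endpoints clearly enough to prevent a wound-level test. If one were run, the nominal 5% would become about 7-27% with three wounds each and 6-17% with two. These figures are illustrative: they assume 10 versus 5 subjects and an ICC of 0.1 to 0.9, and they vanish with one wound each, the only number guaranteed. Second, complete closure has contradictory units and no rule for mixed results. That part needs no assumption; only the size of the resulting difference does.

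The primary safety and feasibility summaries and the serum biomarkers are untouched. Severity is minor to should-fix.

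**What to change.** 1. State in the Summary and sections 4.3, 10.2 and 10.3 that the subject is the unit of inference, with up to 45 wounds from up to 15 subjects. Wound endpoints are compared on one value per subject: the mean over that subject's qualified wounds or, within a mesh stratum, over the wounds of that mesh size. The two-group ANOVA or t-test may then stay. Show the strata side by side and not as independent results, because one subject may enter more than one.
2. Use one subject-level definition of complete closure in the Summary and sections 4.6.2, 8.3 and 10.3.2, with a rule for mixed results that the sponsor chooses before the data are seen. Report any wound-level proportion descriptively or with a cluster-adjusted interval.
3. Apply the change-from-baseline t-test only to endpoints with a scheduled baseline score. For wound scores, either say that there is none or state that the surgery photograph is scored.

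This needs no extra patients, visits or procedures. The price is wider intervals and less favourable p-values on wound endpoints. The grouped subject mean also mixes mesh ratios, so it should be read beside the strata.

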## ABBREVIATIONS

ADRC	Adipose-Derived Regenerative Cells
ADSC	Adipose-Derived Stem Cells
AE	Adverse Event
BARDA	Biomedical Advanced Research and Development Authority
CFU-F	Colony Forming Units Fibroblast
CRF	Case Report Form
DMC	Data Monitoring Committee
DNase	Deoxyribonuclease
ET	Early Termination
FDA	Food and Drug Administration
GCP	Good Clinical Practice
HIV	Human Immunodeficiency Virus
ICH	International Conference on Harmonization
ID	Identification
IRB/EC	Institutional Review Board/Ethic Committee
ITT	Intent-to-Treat
LVL	Low Volume Lipoharvest
PBS	Phosphate Buffered Saline
PI	Principal Investigator
POSAS	Patient and Observer Scar Assessment Scale
PTE	Per-Treatment-Evaluable
SAE	Serious Adverse Event
STSG	Split Thickness Skin Graft
SAP	Statistical Analysis Plan
SD	Standard Deviation
SOC	Standard of Care
SVF	Stromal Vascular Fraction
TBSA	Total Body Surface Area
TF	Tumescent Fluid
UADE	Unanticipated Adverse Device Effects
VAS	Visual Analog Scale
VSS	Vancouver Scar Scale
WHO	World Health Organization

## 1 OBJECTIVE

The objective of the protocol is to evaluate preliminary safety and feasibility of adipose-derived regenerative cells (ADRCs) delivered intravenously for the treatment of full thickness and deep partial thickness thermal wounds in addition to standard of care.

## 2 BACKGROUND

### 2.1 Wounds

Wound healing is a complex multifactorial process involving the interaction of inflammation, granulation tissue formation, re-epithelialization, and angiogenesis. For deep partial thickness and full thickness burns, acute burn management involves multiple activities including protecting the wound from further injury, initial cleansing and debridement, and determination of dressings with or without a topical antimicrobial agent. Fluid resuscitation, prevention of hypothermia and pain management are also critical aspects of management. Surgical procedures involve escharectomy with further debridement and determination of skin grafting (often autologous split thickness skin graft (STSG) or a temporary graft (allograft or xenograft) or a tissue engineered substitute such as Integra®). The use of a tissue engineered substitute/matrix or temporary graft is generally followed by an autologous skin graft. Maturation of the graft may take several weeks and, depending on the severity and location of wound and the degree of meshing required for a STSG, the cosmetic outcome is often unsatisfactory. In addition, complications such as infection or contractures may occur, which can result in further treatments and procedures, as well as prolongation of healing. Furthermore, in the event of a catastrophic event, the current systems may be overwhelmed in the ability to handle substantial numbers of burn cases, which is compounded by the prolonged nature of healing with current techniques and the high level of expertise required to limit complications and increase the likelihood of a satisfactory functional and aesthetic result. Overall, there is a growing need to develop improved techniques in acute burn management.

Adipose Derived Regenerative Cells (ADRCs) are of emerging interest in the application of wound healing. Cells obtained from adipose tissue have been shown to inhibit inflammation, promote angiogenesis, stimulate recruitment of endogenous regenerative cells and promote salvage of damaged cells. On the basis of these properties, several preclinical studies have been performed using freshly isolated and cultured adipose-derived cells in a number of animal models of normal and impaired wound healing. The data consistently show improvement of epithelialization and wound healing. ADRCs are an advantageous resource because they can be found in abundant quantities, they can be harvested with a minimally invasive procedure, and they can be safely and effectively transplanted into an autologous host.

